Bone graft substitute (BGS) materials offer an alternative to autograft bone capable of supporting new bone growth, while avoiding or minimizing the frequent co-morbidities associated with autograft harvest from the iliac crest.³⁻⁵ Allograft bone has been used successfully for more than two decades as a first-generation alternative to autograft bone. While traditional processed allograft bone can be difficult to shape, shows variable resorption characteristics, and variable biological activity, ViviGen® Cellular Bone Matrix has addressed these issues in their product. While containing all the properties required for bone formation, it additionally has a consistency that allows it to hold shape in a putty-like consistency.⁶ ViviGen® Cellular Bone Matrix can be molded into a specific form that allows proper placement, positioning and formation during posterolateral lumbar fusion.⁶

Description of ViviGen®⁶

ViviGen® is manufactured by DePuy Synthes, Inc. (West Chester, Pennsylvania). ViviGen® Cellular Bone Matrix is comprised of cryopreserved viable cortical cancellous bone matrix and demineralized bone. ViviGen® Cellular Bone Matrix is a Human Cells, Tissues, and Cellular and Tissue-based Product (HCT/P) as defined by the U.S. Food and Drug Administration in 21 CFR 1271.3. ViviGen® Cellular Bone Matrix is processed from donated human tissue, resulting from the generous gift of an individual or his/her family.

ViviGen® Cellular Bone Matrix contains all of the properties required for bone formation being that it is osteoconductive, osteoinductive and osteogenic. Safety of ViviGen® Cellular Bone Matrix is defined by every lot is aseptically processed and final product is tested for sterility using USP standards. Packaging and handling is beneficial in that all four sizes of ViviGen® Cellular Bone Matrix will thaw in less than 5 minutes, which is vital for cell viability, in that the ported pouch allows for the quick and efficient removal of the cryopreservation media and rinsing solutions. ViviGen® Cellular Bone Matrix maximizes cell viability by modes of processing that is focused on protecting viable lineage committed bone cells from recovery to implantation.

Objective

The objective of this study is to perform a prospective, randomized, controlled clinical trial to compare radiographic fusion rates and patient reported outcomes, including pain and function preoperatively and postoperatively, using Depuy ViviGen® Cellular Bone Matrix mixed with

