cortical/cancellous allograft in conjunction with an approved Depuy Synthes pedicle screw system compared to autograft mixed with cortical/cancellous allograft in conjunction with the same DePuy Synthes pedicle screw system used for a one or two- level posterolateral lumbar fusion.

Methodology

Study Design

This is a prospective randomized, non-blinded, controlled study. Patients with a diagnosis of degenerative disc disease and/or up to grade I spondylolisthesis and planning to undergo a 1- or 2-level instrumented posterolateral lumbar fusion surgery between L1-S1 will be screened. If eligible and the subject meets all the inclusion criteria and none of the exclusion criteria, the subject will be approached about study participation by the surgeon. If the subject agrees to participate, the consent process will be initiated by the study coordinator. Once the patient has been consented; data including medical history, neurological exam, patient questionnaires (VAS, ODI, SF-36) will be collected. Randomization will occur once a surgery date has been scheduled so the appropriate instrumentation can be boarded accordingly. A randomization envelope will reveal randomization treatment group. The envelopes will be generated in a 1:1 fashion and be randomly allocated to an assigned study identification number. Subjects will be randomized to either: 1) treatment arm where the investigator will use an FDA approved/cleared DePuy Synthes spinal pedicle screw system with ViviGen® Cellular Bone Matrix mixed with cortical/cancellous allograft or the 2) control arm where the investigator use the same DePuy Synthes spinal pedicle screw system with local autologous bone graft mixed with cortical/cancellous allograft. Both treatment groups represent standard of care lumbar fusion surgeries using two types of bone graft options to create the arthrodesis as comparators.

Once the lumbar fusion surgery has taken place as planned; data will be collected regarding the surgery performed, including operative time, amount of bone graft used, spinal system used, length of hospital stay, and adverse events/complications.

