Study subjects will be followed up at 6-weeks, 3-months, 6-months, and 12-months postoperatively at the private practice or clinic. During these routine (standard of care) postoperative visits, subjects will complete questionnaires (VAS, ODI, SF-36, patient satisfaction) and have neurological exam (lumbar spine exam, see appendix 1) completed by the investigator. Adverse events related to device and/or procedure will be evaluated as each postoperative visit. AP and lateral x-rays will be performed at all visits with flexion and extension x-rays added at baseline, 3-months, 6-months, and 12-months. A CT scan of the lumbar spine will be performed during the 12-month postoperative time frame at the Beaumont-RO Imaging Center. Radiographic analysis will be performed and evaluated for fusion status as evidenced by bony bridging, presence of radiolucency, and development of pseudoarthrosis at each follow-up visit.

This study design reflects the current standard of care for lumbar spinal stenosis, degenerative disc disease and lumbar degenerative spondylolisthesis. Lumbar fusion surgery using pedicle screw fixation with autograft and allograft bone grafting options is treatment of choice after conservative (non-surgical) therapies have been implemented and failed.

Statistical Analysis

The sample size will consist of 40 patients; 20 in each treatment arm. The primary hypothesis is that the probability of achieving fusion using ViviGen bone graft is not clinically inferior to using autograft and allograft in lumbar fusion at 12-months post-surgery. Using a one-sided test and fusion rate of 86%, there is a 0.80 probability of 0.80 of finding a difference for 60 patients. A 10% dropout rate was considered. Forty patients may result in low statistical power; however, this may be increased by 10 in each arm once enrollment has obtained and if needed, and upon agreement with study sponsor. Enrollment of 40 reflects the current allotted grant/budget per the study sponsor for this project.

There are other studies that analyzed demineralized bone matrix in two-year fusion outcomes for lumbar spinal fusions that used a similar size population (range between 13 and 28 patients) to the proposed enrollment for this study, as demonstrated in *Vaccaro et al (2007)* and *Kang et al (2012)*. Power calculation for the primary outcome of bone fusion was obtained using PASS 15. An 86% fusion rate (Kang et al) was assumed with a 10% dropout rate for both arms.

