Secondary endpoints (VAS, ODI, SF-36, neurological status, and fusion) will be quantified to detect changes longitudinally from baseline through 12-months post-surgery.

Study Population and Inclusion/Exclusion Criteria

Patients with a diagnosis of spinal stenosis, degenerative disc disease and/or up to grade I spondylolisthesis and planning to undergo a 1 or 2-level instrumented posterolateral lumbar fusion surgery between L1-S1 will be asked to participate in the study. If eligible, the consent process will be initiated by the study coordinator

A subject may be included if the following criteria are met:

1. ≥ 18 years of age
2. Able to provide consent
3. Is undergoing standard of care one or two-level instrumented posterolateral fusion at the level between L1-S1
4. Has diagnosis of spinal stenosis, degenerative disc disease and/or up to Grade 1 spondylolisthesis
5. Requires decompression at intended fusion level (multi-level decompression allowed L1-S1)
6. Has failed 6-weeks or more of conservative, non-operative treatment
7. Has back and/or radicular lumbar symptoms with ODI (Oswestry Disability Index) score of ≥ 30 preoperatively.

A subject will be excluded if any of the following criteria are met:

1. Any prior lumbar fusion surgery
2. Requires fusion of more than two levels
3. Requires an interbody fusion based on relevant diagnosis and factors (such as foraminal stenosis, degree of spondylolisthesis, spinal deformity, disc space collapse, and subject's age) as determined by investigator
4. BMI > 40

5. Active systemic infection or infection at operative site
6. History of an osteoporotic fracture and/or vertebral body fracture
7. Is currently being treated with chemotherapy, radiation, immunosuppression or chronic steroid therapy
8. History of osteoporosis, osteopenia, or osteomalacia that would contraindicate spinal surgery
9. Psychological or physical condition in the opinion of the investigator that would interfere with subject self-assessments
10. History of neurological condition in the opinion of the investigator that may affect lumbar function and pain assessments
11. Subjects with a history of cancer must be disease free for at least 3 years
12. Pregnant, or plans on becoming pregnant

Intervention

Treatment arm/group: 20 subjects undergoing open, one or two-level instrumented posterolateral lumbar fusion surgery using ViviGen Cellular Bone Matrix mixed with cortical/cancellous allograft and DePuy Synthes pedicle screw system.

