Control arm/group: 20 subjects undergoing open, one or two-level posterolateral lumbar fusion surgery using local autograft mixed with cortical/cancellous allograft and DePuy Synthes pedicle screw system.

Data and Safety Monitoring

The PI and study team (including sub-investigators, clinical research manager) will be responsible for data and safety monitoring. All adverse events will be reviewed to determine relatedness to the product and reported to sponsor as necessary (if related to product and unanticipated according to risk profile). The data will be reviewed for maintenance of confidentiality and integrity as well as the data collection process. The data and safety review will take place every six months from the date of the first patient enrolled into the study or after every ten patients enrolled whichever comes first.

Adverse Events

Relevant adverse events (those related to the study device, the surgical procedure, or the lumbar spine) will be recorded in this study. All adverse events will be reviewed for relatedness and expectedness by the PI on a case by case basis and per Data and Safety Monitoring guidelines.

Protocol Deviations

The investigators are responsible for documenting all protocol deviations, including an explanation for why the deviation occurred. All protocol deviations will be recorded and submitted to the IRB per policy.

Outcomes

Primary Endpoint

IRB NUMBER: 2018-158

IRB APPROVAL DATE: 10/18/2019

- Successful lumbar fusion as measured by CT scan and flexion/extension x-rays at 12-months; as evidenced by bony bridging, presence of radiolucency, no development of pseudoarthrosis

Secondary Endpoints

- Improvement in patient reported outcomes as measured by VAS (\geq 2-point improvement), ODI (\geq 15-point improvement), SF-36 (\geq 15-point improvement) from baseline to 12-months.
- No new or worsening neurological (motor and sensory) deficit as compared to baseline through 12-months. No revision surgery and/or development of pseudoarthrosis by month 12.
- No occurrence of adverse events related to device by month 12.

Subject Screening and Enrollment

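### The Objective promises a between-arm comparison of patient-reported outcomes, but the only stated secondary analysis is change from baseline, and satisfaction has no baseline score to be compared with

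*Combined protocol and SAP*

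**What the plan says.** The Objective is to "compare radiographic fusion rates and patient reported outcomes, including pain and function preoperatively and postoperatively", with ViviGen plus allograft "compared to autograft mixed with cortical/cancellous allograft in conjunction with the same DePuy Synthes pedicle screw system". The Study Design section randomises 1:1 and describes both arms as standard-of-care surgery "using two types of bone graft options to create the arthrodesis as comparators".

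The only analysis sentence for the secondary endpoints, at the end of the Statistical Analysis section, lists VAS, ODI, SF-36, neurological status and fusion and says they "will be quantified to detect changes longitudinally from baseline through 12-months post-surgery". It names no arm, effect measure, model, test or interval. The only between-arm hypothesis in that section is the primary one, on fusion at 12 months.

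The Secondary Endpoints list under Outcomes begins "Improvement in patient reported outcomes as measured by VAS" and gives thresholds from baseline to 12 months: at least 2 points for VAS, 15 for ODI and 15 for SF-36. The synopsis repeats them. Secondary objective 1 in the synopsis groups patient satisfaction with the three instruments and sets postoperative scores against preoperative ones.

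On data collection, the Study Design section says that after consent "patient questionnaires (VAS, ODI, SF-36) will be collected". At the follow-up visits, "subjects will complete questionnaires (VAS, ODI, SF-36, patient satisfaction" and so on. The visit schedule in the synopsis agrees: satisfaction is absent at baseline and appears from the 6-week visit.

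**The concern.** The randomised question about patient-reported outcomes is whether patients do differently with one graft than with the other. The stated analysis answers another question: whether patients change after surgery. Every patient has decompression and instrumented fusion, and entry requires an ODI of at least 30, so improvement can be expected in both arms whatever the graft. Followed literally, the plan could report favourable change in each arm and leave the comparison in its own Objective unanswered. Two favourable within-arm results also invite a reading of similarity that they do not support.

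The trial is non-blinded and these outcomes are self-reported. That is a further reason to write the contrast down before the data are seen.

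The satisfaction wording is a separate and smaller matter: the synopsis asks for a comparison with a score that the schedule does not collect.

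**Working it through.** The plan gives no figure for the secondary endpoints. Its single power statement concerns fusion and plays no part here. The point rests on the text; the arithmetic only shows what the corrected analysis could deliver.

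**1. Comparator named in each place, for patient-reported outcomes**
- Objective: the autograft arm.
- Study Design: two grafts as comparators.
- Statistical Analysis: baseline.
- Synopsis, secondary objective 1: baseline.
- Outcomes, Secondary Endpoints: improvement from baseline past a threshold, with no mention of arm.

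In the Objective, the reference to before and after surgery says when outcomes are measured. The sentence then goes on to name the autograft arm as comparator. No analysis statement carries that comparator forward.

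**2. What change from baseline estimates**

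Let S be the mean change due to everything common to both arms (decompression, fixation, time, selection on a high ODI), and G the extra effect of ViviGen over autograft.
- Mean change, ViviGen arm: S + G
- Mean change, control arm: S
- Difference: (S + G) − S = G

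Only the difference isolates G. As an illustration with assumed inputs, take G = 0, a mean ODI improvement of 20 and an SD of change of 15, normally distributed. Reading the threshold per patient, 1 − Φ((15 − 20)/15) = 0.63, so about 63% of each arm would pass it while the difference between arms is 0.

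**3. Satisfaction**
- Baseline: VAS, ODI and SF-36 only (Study Design; synopsis schedule).
- 6 weeks, 3, 6 and 12 months: the same three plus satisfaction.

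There is no preoperative satisfaction score to compare with.

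**4. Precision of the corrected contrast**

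Evaluable per arm: 20 × 0.9 = 18, using the plan's 10% dropout. If the optional increase of 10 per arm is used: 30 × 0.9 = 27.

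Difference in responder proportions, Wald 95% half-width = 1.96 × √(2P(1 − P)/n), with rate P assumed equal in both arms:
- n = 18, P = 0.5: 1.96 × √(0.50/18) = 32.7 points
- n = 18, P = 0.8: 1.96 × √(0.32/18) = 26.1 points
- n = 27, P = 0.5: 1.96 × √(0.50/27) = 26.7 points
- n = 27, P = 0.8: 1.96 × √(0.32/27) = 21.3 points

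Newcombe intervals at n = 18 with equal observed counts are close to this: ±29.7 points for 9/18 in each arm and ±26.5 for 14/18.

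Baseline-adjusted ODI difference, half-width = t(2n − 3) × SD × √(2/n). For n = 18, t(33) = 2.03 and √(2/18) = 0.333. With assumed residual SD:
- 12: 8.1 points
- 15: 10.2 points
- 20: 13.6 points

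**5. Gain from adjusting for baseline**

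The variance of the ANCOVA estimate relative to the change-score estimate is (1 − ρ²)/(1 + k² − 2ρk), where ρ is the correlation of baseline with 12-month score and k is baseline SD over 12-month SD. For assumed ρ of 0.3 and 0.7 this gives 0.65 and 0.85 at k = 1, and 0.85 and 1.00 at k = 0.7. The reduction in variance is therefore between 0 and 35%.

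**The case against.** The strongest reply is that this is under-specification rather than a wrong analysis. The Objective states the comparison, the design randomises to two comparators, and the sentence in the Statistical Analysis section may describe the variable (change) rather than the contrast. A between-arm comparison of change would be consistent with it. That stands: a reader might infer that the plan prescribes within-arm testing only, or excludes a comparison by arm, and the documents support neither. But an implied contrast is not a stated one. The plan does state a between-arm hypothesis for fusion, whereas for patient-reported outcomes the synopsis names a different comparator.

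Further objections, and what stands of each:
- A reader might take the thresholds as fully defined responder endpoints. The documents do not say whether they apply per patient or to a group mean, nor which VAS item or SF-36 score is meant. The responder figures above therefore rest on a reading that the sponsor must confirm.
- A reader might take the wide intervals as the size of the error. They follow from the sample size and describe the corrected analysis.
- A reader might assume fewer than 18 evaluable per arm, because the Screen Failures section drops patients whose surgery changes intraoperatively. The documents give no number and do not say whether such patients are replaced, so no smaller case is used.
- ANCOVA and Newcombe are choices among reasonable methods, and the precision gain from ANCOVA may be nil. This is fair; the essential step is to state the contrast.
- Satisfaction appears in an objective and not in the analysis or endpoint lists, so this is a correction of wording. That is also fair, but the comparison as worded still cannot be made.

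**Conclusion.** The point holds in a limited form. The Objective calls for a between-arm comparison of patient-reported outcomes, the stated analysis and the synopsis objective use baseline as comparator, and no between-arm contrast is stated for these endpoints. Change from baseline alone does not isolate the graft effect. The comparison of satisfaction with baseline cannot be made, because no baseline score is collected. Both conclusions rest on the text and need no numerical assumption.

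Severity is minor. Only secondary endpoints are affected, and a reader should not infer that the primary fusion comparison is in doubt on this ground. No size can be put on the defect itself. After correction, the 95% half-widths would be about 26 to 33 percentage points for a responder difference (assumed rates 80% to 50%) and 8 to 14 ODI points (assumed residual SD 12 to 20) with 18 per arm. With 27 per arm, the responder half-width would be about 21 to 27 points. At that precision, a finding of no clear difference would not be evidence of equivalence.

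**What to change.** Amend the secondary-endpoint sentence in the Statistical Analysis section and secondary objective 1 in the synopsis:
- For VAS, ODI and SF-36, state the analysis as the ViviGen-minus-control difference at 12 months with a 95% confidence interval, adjusted for the baseline score (ANCOVA). Name the VAS item and SF-36 score meant.
- Confirm whether the improvement thresholds apply per patient. If so, also give the between-arm difference in proportions meeting each one, with a small-sample interval such as Newcombe.
- State the neurological endpoint in the same way, as a between-arm difference in proportions.
- Keep within-arm change over time as descriptive.
- Delete the comparison with baseline for satisfaction and compare it between arms at the postoperative visits.
- Present all of these as estimates, not as evidence of equivalence.

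The cost is a short amendment submitted to the IRB. No visit or questionnaire is added, since VAS, ODI and SF-36 are already collected in both arms at baseline and at every follow-up. The downside is that the estimates will be imprecise, and the report should say so.

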| Study Summary | 
All subjects who sign an IRB approved consent form are considered in active screening to determine eligibility. Once a subject is consented, the following visits will take place:
 
Baseline (\leq 60 days of surgery):
 
 • Medical history • Neurological exam (Lumbar Spine Exam, appendix 1) • Demographics • VAS, ODI, SF-36 questionnaires • Lumbar spine x-rays AP/lateral, flexion/extension or as done per standard of care • Randomization 
Surgical Visit:
 
 • Surgery performed • Operative Time • Amount of Bone Graft used • Pedicle Screw System used • Length of Hospital Stay • Adverse Events/Complications 
6-week Visit (\pm 2 weeks):
 
 • VAS, ODI, SF-36, patient satisfaction questionnaires • Neurological Exam • Lumbar AP/Lateral x-rays • Adverse Events 
3-month Visit (\pm 3 weeks):
 
 • VAS, ODI, SF-36, patient satisfaction questionnaires • Neurological Exam • Lumbar AP/Lateral and flexion/extension x-rays • Adverse Events 
6-month Visit (\pm 1 month):
 
 • VAS, ODI, SF-36, patient satisfaction questionnaires • Neurological Exam • Lumbar AP/Lateral and flexion/extension x-rays • Adverse Events 
12-month Visit (\pm 2 months):
 
 • VAS, ODI, SF-36, patient satisfaction questionnaires • Neurological Exam • Lumbar AP/Lateral and flexion/extension x-rays • CT scan of the lumbar spine without contrast • Evaluate fusion status • Adverse Events |
|---------------|---|

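### The only definition of successful fusion lists radiolucency as evidence of success, and nothing in the plan says how radiolucency should be scored

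*Combined protocol and SAP*

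**What the plan says.** The primary endpoint appears twice, under Outcomes (Primary Endpoint) and in the Study Synopsis (Study Endpoints). Both define successful fusion at 12 months on CT and flexion/extension x-rays, "as evidenced by bony bridging, presence of radiolucency, no development of pseudoarthrosis".

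Three other places bear on how fusion is judged:

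- **Study Design:** the radiographs are to be "evaluated for fusion status as evidenced by bony bridging, presence of radiolucency, and development of pseudoarthrosis at each follow-up visit". This lists what to look at and states no rule for success.
- **Study Synopsis, 12-month visit:** the instruction is only "Evaluate fusion status".
- **Statistical Analysis, closing paragraph on secondary endpoints:** "Secondary endpoints (VAS, ODI, SF-36, neurological status, and fusion) will be quantified to detect changes longitudinally". Fusion is named here as a longitudinal outcome, with no rule of its own.

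The secondary endpoints, by contrast, are worded so that each adverse finding must be absent. One reads "No revision surgery and/or development of pseudoarthrosis by month 12"; the neurological and device-related adverse event endpoints are negated in the same way.

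**The concern.** The endpoint looks like the Study Design list turned into a success rule by negating its last item only. Bridging counts for fusion and pseudoarthrosis counts against it, but radiolucency is left standing as a finding whose presence supports success. Since every other adverse finding among the endpoints is negated, a dropped negation is the likeliest explanation.

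This is the trial's only definition of the outcome on which its primary non-inferiority hypothesis rests. If the definition gives the wrong direction for one of its three components, or none, whoever reads the images must supply the rule, and the reported 12-month fusion rate depends on that unplanned choice. The study is not blinded, which is a further reason to settle the rule in advance, although no bias between the arms is claimed here.

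**Working it through.** **1. The plan's own figure.** The Statistical Analysis section claims 0.80 power with 60 patients ("Using a one-sided test and fusion rate of 86" percent). It states neither a margin nor alpha, so the claim can be neither confirmed nor refuted. Solving margin = (z(1−α) + z(0.80)) × √(2 × 0.86 × 0.14 / n) at n = 30 per arm gives 22.3 points for one-sided α = 0.05 and 25.1 points for α = 0.025. At n = 27, after 10% dropout, the margins are 23.5 and 26.5 points. This is context only; the present point does not depend on it.

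**2. The passages side by side.**

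| Place | Bridging | Radiolucency | Pseudoarthrosis | Combination rule |
|---|---|---|---|---|
| Study Design | listed | listed, no direction | listed, no direction | none |
| Outcomes, Primary Endpoint | counts for success | presence counts for success | must be absent | none |
| Synopsis, Primary Endpoint | counts for success | presence counts for success | must be absent | none |
| Synopsis, 12-month visit | – | – | – | none |
| Statistical Analysis, longitudinal fusion | – | – | – | none |

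The identical wording in two sections makes a fault in text extraction an unlikely explanation. No section grades radiolucency or sets a tolerance.

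**3. The possible readings.**

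- *Literal, all items required:* a bridged patient without lucency or pseudoarthrosis does not qualify.
- *Neutral list:* the definition of success contains an item with no stated direction.
- *Corrected by the reader:* lucency is either ignored or scored as adverse to some degree, and the plan does not say which.

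**4. Illustration of size.** Inputs from Statistical Analysis are 20 patients per arm ("The sample size will consist of 40 patients; 20 in each treatment arm"), 10% dropout ("A 10% dropout rate was considered") and a fusion rate of 86%. The share r, radiolucency among patients bridged without pseudoarthrosis, is assumed because the documents give none.

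Evaluable per arm = 20 × 0.90 = 18. One patient = 1/18 = 5.6 points.

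*Case A: 86% are bridged without pseudoarthrosis before lucency is considered.* The rate with lucency ignored is 86%. With any lucency scored as failure it is 0.86 × (1 − r). If lucency were literally required it would be 0.86 × r.

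| r (assumed) | Ignored | Scored as failure | Gap (0.86 × r) | Gap × 18 | Literally required |
|---|---|---|---|---|---|
| 0 | 86.0% | 86.0% | 0 points | 0 patients | 0% |
| 0.10 | 86.0% | 77.4% | 8.6 points | 1.5 patients | 8.6% |
| 0.30 | 86.0% | 60.2% | 25.8 points | 4.6 patients | 25.8% |

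The gap reaches one patient per arm at r = 1/(0.86 × 18) = 0.065.

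*Case B: the cited 86% already excludes patients with lucency.* The rate with lucency scored as failure stays at 86%. With lucency ignored it is 0.86/(1 − r), and r cannot exceed 0.14.

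| r (assumed) | Scored as failure | Ignored | Gap | Gap × 18 |
|---|---|---|---|---|
| 0 | 86.0% | 86.0% | 0 points | 0 patients |
| 0.10 | 86.0% | 95.6% | 9.6 points | 1.7 patients |
| 0.14 | 86.0% | 100% | 14.0 points | 2.5 patients |

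**The case against.** The strongest reply is that the intended sense is obvious. If the document itself shows that a negation was dropped, no competent reader will score lucency as success, and this is a drafting slip, with one definition applied to both arms. It is also fair to say that:

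- the literal reading excludes bridged patients without lucency only if all items are required, which the plan does not state;
- a reader might grade lucency or weigh the features together, so ignoring it and treating any lucency as failure are not the only options;
- r is invented, and its plausible size depends on how far lucency and pseudoarthrosis overlap;
- the plan allows 10 more patients per arm. At 30 less 10%, one patient is 1/27 = 3.7 points rather than 5.6.

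Much of this stands as a limit on the numbers. The figures show sensitivity and are not a forecast, and the literal consequence is conditional on the items being joint requirements, although a comma-joined definition reads most naturally that way. None of it supplies the missing rule. A reader who recognises the slip must still decide whether lucency counts and how much is tolerated. Graded reading is one more unplanned choice. Nothing in the plan says that pseudoarthrosis subsumes radiolucency, which is listed separately each time.

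**Conclusion.** The concern holds. The sole definition of the primary outcome gives radiolucency in what is apparently the wrong direction, or in no usable direction, and no other section repairs it. That a negation was dropped is an inference from the surrounding text. The rule is unusable with or without that inference.

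The seriousness comes from where the defect sits, in the primary endpoint, and not from a demonstrated numerical effect. Under the assumed lucency shares, the choice between ignoring lucency and scoring it as failure moves the fusion rate by 0 to 25.8 points if the 86% is counted before lucency (r from 0 to 0.30), and by 0 to at most 14 points if the 86% already excludes it. At r = 0 there is no effect. It should be fixed before the 12-month endpoint is read.

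**What to change.** Before any 12-month images are read, reconcile the sections as follows:

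1. In the Primary Endpoint text under Outcomes and in the Synopsis, replace the radiolucency item with its absence, or with the investigators' own stated tolerance for which radiolucency counts.
2. State in both places that all listed items must hold for success.
3. Keep the Study Design list as the features to be scored, and refer the Synopsis 12-month instruction to the corrected rule.
4. In Statistical Analysis, state how radiolucency is scored when fusion is followed longitudinally.
5. Report the 12-month fusion rate with the radiolucency item ignored as a sensitivity analysis.

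The documents do not give enrolment status. If reading has already begun, the change should be dated and all images scored under the one rule.

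The cost is a wording edit in two places, a short addition in two others and one agreed statement on lucency, with no extra procedures. The downside is that, if the 86% does not already exclude lucency, the expected fusion rate and therefore the power may be somewhat lower than planned. That loss cannot be computed without a margin, an alpha and a lucency rate. A stated tolerance for minor lucency would limit it.
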